Aim 1: The primary outcome measure will be gait velocity, which is directly linked to disability and social re-integration after stroke. Gait velocity will be assessed by measuring the time to traverse the middle 6 m of a 10-m walkway (5 repetitions/assessment). Secondary outcomes include: 1. Gait endurance: The distance walked over 6 minutes. 2. Fall Frequency: Number of falls experienced weekly. 3. Leg Motor Fugl-Meyer (FM) Score: Assessed according to the FM rating system. 4. Dorsiflexion Active Range of Motion (AROM) and torque: The paretic foot will be placed in an articulated brace which maintains the ankle at neutral during idling, while fixing the tibia perpendicular to the ground and the femur horizontal to the ground. The brace will be instrumented with an electro-goniometer and torque meter to automatically measure the maximum dorsiflexion AROM and torque (over 3 trials). 5. EEG Map: Subjects will undergo 64-channel EEG recording as they engage in 100 alternating 10-s long epochs of idling and attempted dorsiflexion. The EEG ERD/ERS, defined as the drop/rise in alpha (8-12 Hz) and beta (13-30 Hz) band power during attempted dorsiflexion (compared to idling), will be calculated and averaged over all epochs and across all channels. A pre-intervention baseline for each outcome will first be established. Subsequently, measurements will be performed at 1 week intervals during the intervention phase (total of 3), immediately after the intervention phase, as well as 1 and 3 months after completion of interventions. The primary efficacy outcome and endpoint will be gait velocity immediately after the intervention phase. Aim 2 (subgroup analysis of Phase II clinical trial) Since stroke is a heterogeneous disease, responsiveness to rehabilitation therapy is not uniform across all subpopulations. Hence, it is important to ensure that any new therapy, e.g. BCI-FES therapy, is matched to subpopulations that will benefit the most. The following set of baseline characteristics will be assessed during the pre-intervention phase (Fig. 6, Phase 2) for Groups 1 and 2 to determine which features influence responsiveness to BCI-FES therapy: 1. Baseline gait velocity, dorsiflexion AROM and torque: Baseline gait velocity and dorsiflexion AROM and torque will be taken from Aim 1. 2. TA volitional electromyogram (EMG): TA EMG will be assessed by having subjects attempt dorsiflexion while seated with tibia perpendicular to ground. EMG will be acquired by a bioamplifier with surface electrodes placed over the TA muscle. Subjects will be categorized as either

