#### **Statistical Considerations**

Is a statistical analysis plan appropriate for this qualitative study design?

Yes

Describe the statistical methods for the stated specific aims and hypotheses. Your analysis plans should match the stated study specific aims and hypotheses:

Aim 1: The study design is a parallel randomized controlled trial with two arms: BCI-FES dorsiflexion therapy and dose-matched conventional physical therapy. A total of 80 subjects (which includes 10% attrition) will be randomized with 1:1 ratio into the two study arms. The primary outcome is gait velocity and the secondary outcomes are gait endurance, fall frequency, leg motor FM score, and dorsiflexion AROM and torque. Outcomes measures will be evaluated at baseline, weekly during therapy, immediately post-intervention, and 1- month and 3-months post-therapy. The primary efficacy analysis (with intent-to-treat analysis with respect to treatment randomized) will be based on a linear mixed model (LMM) with gait velocity measured at baseline weeks 1-4 (time 0, 1, 2, 3, and 4) with time, treatment group and group by time interaction assess the difference in the rates of change (improvement) in gait velocity between treatment groups. Model estimation will be based on restricted maximum likelihood (REML) with unstructured covariance among repeated measurements over time. The LMM will also be applied to evaluate group difference for secondary outcomes and secondary endpoints at 1- and 3-months post-therapy. In order to determine if  $\mu$  and  $\beta$  ERD/ERS significantly changes over the 4 weeks of therapy, the ERD and ERS magnitude will be calculated for each EEG channel across all attempted dorsiflexion epochs, and for each assessment. The Mann-Whitney U test will be used to determine if any significant changes in the magnitude of ERD/ERS at each assessment with respect to the baseline. Based on the findings, each subject will be categorized as demonstrating significant changes in ERD/ERS or not. Next, all subjects will also be categorized on whether they experienced a detectable increase in gait velocity (defined as an increase in gait velocity of  $>0.16$  m/s with respect to baseline). A Chi-square test will be used to assess if there is a difference between the proportion of those with changes in ERD/ERS magnitude in those who had gait improvement within the BCI- FES therapy group. This will also be repeated for the control group. In addition, to determine if the presence of significant ERD/ERS changes was affected by group, the Chi-square test will be repeated by using BCI-FES group as the observation and the control group as the expected values. Aim 2: Data from Aim 1 will be used for analysis in this aim. The primary outcome is gait velocity immediately post-BCI-FES therapy, and the secondary outcomes are the same as in Aim 1. To test whether specific stroke features (e.g. baseline gait velocity, dorsiflexion AROM, etc.) modify response to treatment over

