
treatment duration, a LMM model with three-way interaction (group, time, modifying factor) will be used to test whether the slope of the three-factor interaction is zero (specific stroke feature does not modify response to treatment). Aim 3: The aim is designed as a randomized controlled study with two arms: BCI-FES dorsiflexion therapy and BCI-robotic orthosis therapy. A total of 20 subjects will be recruited and randomized with 1:1 ratio into the two arms. The primary outcome is gait velocity, and the secondary outcomes are ankle torque and active range of motion. The main interest is to evaluate if the correlation between  $M1 \rightarrow \text{EMG}$ ,  $w$ , (normalized range: 0-1), and gait velocity is different between the two study groups averaged over time after treatment, adjusted for baseline outcome measure. For example, with outcome gait velocity, the analysis will be based on a regression model with group,  $w$ , and their interaction, adjusted for baseline gait velocity. The relationship between both  $w$  with secondary outcomes will be similarly analyzed.

Describe the statistical method(s) that will be used to analyze the primary outcome(s) or endpoints:

The primary statistical methods for primary outcome, gait velocity, is already described in Aim 1 above.

If appropriate describe secondary or post hoc analyses of primary outcome(s) or other exploratory analysis and if necessary, provide a breakdown of the methods used per outcome or endpoint:

The statistical method for secondary outcome measures is similar to the primary outcome, and is already described in Aim 1 and 2 above.

**Sample Size Determination:** Explain how the overall target sample size was determined (e.g., power analysis; precision estimation), providing justification of the effect size for the primary outcome based on preliminary data, current knowledge/literature and/or cost consideration; if appropriate, provide sample size justification for secondary outcomes. Power analysis should (at least) match the primary outcome/endpoint:

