**Power Analysis:** For Aims 1 and 2, the power analysis was based on a LMM with two treatment groups and 5 repeated measures (baseline and after weeks 1-4) with a significance level of 0.05. Previous studies have examined the clinically meaningful gait improvement (minimal clinically important difference) of 0.16 m/s, including a multicenter randomized clinical trial that includes conventional physical therapy. Thus, to ensure clinically meaningful effect size, we assume conventional therapy will have an improvement of 0.25 m/s after 4 weeks of treatment. Data from prior studies as well as our own preliminary data (n=9) found that the between-subject variance in gait velocity of about 0.16 m/s and the within-subject correlation of about 0.95. Table 1 below shows the power to detect improvement of BCI-FES over conventional therapy of 30% - 40%. Thus, for the proposed study with n=80 patients (40 per arm) has 92% to 94% power to detect an effect size/improvement of 35% for various between-subject variance (0.15 m/s to 0.17 m/s) in determining treatment efficacy (Aim 1). We note that n=80 total has been intentionally inflated in order to accommodate the objectives of aim 2 to examine modifying factors, such as TA MEP (primary modifying factor), on treatment. That is, for n=30 per arm the power to determine efficacy (aim 1) is 85% for detecting an effect size/improvement of 35% (between-subject variance 0.16 m/s); thus, increasing to n=40 allows for detecting modifying factor on treatment (aim 2) when the interaction effect smaller (effect size 28% can be detected with 79% power). Table 1: Power to detect improvement in gait velocity due to BCI-FES over conventional therapy for n=80 with various between-subject variance (aim 1). Between-Subject Variance Effect Size (Improvement) 0.15 0.16 0.17 30% 87.3% 85.2 % 83.0% 35% 94.5% 93.5% 92.1% 40% 98.3% 97.7% 97.0% Aim 3: Total sample size of n=20 will have 82% power to detect an R-square of 0.16 (attributed to the effect of interest, e.g., w x group) adjusted for baseline measurement and main effects whose total contribution R-square is 0.5 (for 3 independent variables) in a multiple regression model.

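### Aim 2 uses baseline gait velocity both as modifier and as the time-0 response; with a continuous modifier and Aim 1's unstructured covariance, the REML fit has no maximum

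*Combined protocol and SAP*

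**What the plan says.** Under Statistical Considerations, Aim 2 has no data of its own: "Data from Aim 1 will be used for analysis in this aim". The purpose is given as "To test whether specific stroke features (e.g. baseline gait velocity, dorsiflexion AROM, etc.) modify response to treatment over" the treatment period. The method is that "a LMM model with three-way interaction (group, time, modifying factor) will be used to test" for effect modification, and the question put to the model is "whether the slope of the three-factor interaction is zero". Study Design confirms that the modifier is not a separate measurement: "Baseline gait velocity and dorsiflexion AROM and torque will be taken from Aim 1".

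The mixed model is specified once, under Aim 1. Its response is "gait velocity measured at baseline weeks 1-4 (time 0, 1, 2, 3, and 4", so the baseline value is the first element of each participant's response vector. Estimation is also given there: "Model estimation will be based on restricted maximum likelihood (REML) with unstructured covariance among repeated measurements over time". The power section applies the five-measure layout, baseline plus four weekly values, to both aims: "For Aims 1 and 2, the power analysis was based on a LMM with two treatment groups and 5 repeated measures (baseline and after weeks".

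The Aim 2 text does not remove time 0, name another covariance or give a cut-point for baseline gait velocity. Its primary outcome is gait velocity right after therapy ends. The power section names TA MEP as the primary modifying factor.

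**The concern.** When the modifier is baseline gait velocity and the outcome is gait velocity, the same number stands on both sides of the model at time 0. A regression that includes the modifier predicts that response exactly. An unstructured covariance gives time 0 a variance of its own, and nothing stops the fit from driving that variance to zero.

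Baseline gait velocity is named first in both the Aim 2 hypothesis and the Aim 2 analysis. With low AROM, it carried the pilot's subgroup signal. According to the Progress Report, enrolment is closed and data analysis belongs to the next approval period. If the model fails then, someone must choose another covariance, another coding of the modifier or another set of time points. Those choices do not have the same power.

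**Working it through.** **Inputs.** From the power section: between-subject variance 0.16, within-subject correlation 0.95, control improvement 0.25 m/s over 4 weeks, 40 per arm, two-sided 0.05. From the Progress Report: 62 randomised in Aim 1.

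**1. Is baseline a response in the planned model?** Test the difference in slopes over t = 0, 1, 2, 3, 4, where the sum of squared deviations of t is 10.
- SD of a participant's slope = sqrt(0.16 x 0.05 / 10) = 0.0283.
- For a 35% effect, delta = 0.35 x 0.25 / 4 = 0.0219 per week.
- With 40 per arm, SE = 0.0283 x sqrt(2/40) = 0.00632 and power = 93.3% (plan: 93.5%).
- With 30 per arm, power = 85.0% (plan: 85%).
- For a 28% effect with 40 per arm, power = 79.0% (plan: 79%).

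All nine cells of Table 1 reproduce within one percentage point, so the planned model does count baseline among its responses. This formula implies compound symmetry.

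**2. Algebra.** Let m be the modifier and g the group. At time 0 the model is b0 + b1 g + b2 m + b3 g m, and the response is m. Setting b0 = 0, b1 = 0, b2 = 1, b3 = 0 makes every time-0 residual zero. Apart from a constant, the REML log-likelihood is

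-1/2 [ n ln|S| + ln|X'V^-1 X| + r'V^-1 r ].

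Give time 0 the variance s, uncorrelated with the weeks 1-4 block, and let s fall:
- the first term contributes n ln(s);
- the four coefficients fixed by the time-0 data contribute -4 ln(s);
- the time-0 part of the residual term is zero.

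The log-likelihood therefore grows as -(n - 4)/2 x ln(s). Per 100-fold fall in s:
- n = 62: 29 x 4.605 = 133.5;
- n = 80: 38 x 4.605 = 175.0.

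**3. Numerical check.** One data set was simulated with n = 80, variance 0.16 and correlation 0.95, using the time-0 response as modifier:

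| s | REML, linear time | REML, categorical time |
|---|---|---|
| 1e-2 | 726.2 | 698.4 |
| 1e-4 | 901.9 | 873.4 |
| 1e-6 | 1076.9 | 1048.4 |
| 1e-8 | 1251.9 | 1223.4 |
| 1e-10 | 1426.9 | 1398.4 |

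A free fit of the unstructured covariance failed, with s near 1e-12 (linear time) and 1e-19 (categorical time). The interaction at week 4 settled at -0.130 (linear) and -0.157 (categorical). The likelihood and the covariance estimate break down; the interaction estimate does not.

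**4. Which specifications do fit?** On the same data, each of these reached a finite maximum:
- a different continuous modifier;
- baseline dichotomised at 0.4 m/s;
- compound symmetry in place of unstructured;
- weeks 1-4 only, with baseline as covariate and modifier (REML 559.9 with linear and 544.5 with categorical time; smallest covariance eigenvalue about 0.004).

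In the last fit with categorical time, the week-4 estimate was again -0.157.

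**5. Are the repairs interchangeable?** I simulated 10,000 trials per setting at n = 62 with the same variance and correlation. The assumed modification was 0.15 m/s per m/s of baseline at week 4, growing linearly from week 0. Compound symmetry with linear time rejected in 52% of trials, and week-4 regression on baseline, group and their product in 43%. With no modification, both rejected in about 5%. Both are valid here, but they differ in power.

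**The case against.** **The failure needs two conditions that Aim 2 does not state.** The covariance sentence sits under Aim 1, and Aim 2 asks only for a mixed model. The word slope may refer to slope over time and not to a continuous modifier; the pilot's signal was dichotomised, and TA EMG is categorised. Compound symmetry or a dichotomised baseline gives a finite fit. This stands, and the point is conditional on both. Still, the plan specifies no other mixed model, and it gives no Aim 2 cut-point for baseline gait velocity, so the failing version is the most direct reading.

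**The reach is small.** This stands too. A reader might infer that the primary efficacy result or Aim 2 as a whole is undermined. The documents do not support that: Aim 1's primary model has no baseline modifier, the primary modifying factor is TA MEP, and baseline AROM or torque as a modifier of gait velocity is not degenerate.

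**Regression to the mean.** A reader might also infer that it biases the planned test. It does not. In a randomised comparison it is the same in both arms, so it enters time-by-modifier and not the three-way term. Simulated under compound symmetry with linear time, the three-way term averaged 0.000, with type I error of 5.1% at n = 62 and 5.0% at n = 80.

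**The failure would be visible.** Non-convergence would show in any dry run on simulated or arm-masked data, before results are known, and the repair is simple. That lowers the risk of a silent error. It does not settle which repair is used, and step 5 shows that the choice affects power.

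**Conclusion.** The point holds in conditional form. If Aim 1's unstructured covariance carries over to Aim 2 and baseline gait velocity enters as a continuous modifier with its lower-order terms, the specified REML fit has no maximum. The log-likelihood climbs by 133.5 (n = 62) or 175.0 (n = 80) for every 100-fold fall in the time-0 variance. The same algebra applies to AROM or torque modelled on its own baseline. The stronger statement, that the analysis cannot be fitted under any reading, is not supported. Nor is any claim of a biased interaction estimate, since the estimate stays finite. This is a specification gap in a secondary aim. It deserves closing because it concerns a named modifier and the available repairs differ in power.

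**What to change.** Limit the change to models in which the modifier is the outcome's own baseline: gait velocity, AROM and torque. For these, the SAP should:
- take time 0 out of the response and model weeks 1-4 by REML with unstructured covariance;
- include baseline, group, visit, group-by-visit, baseline-by-visit, group-by-baseline and group-by-baseline-by-visit, with baseline continuous;
- test the group-by-baseline contrast at week 4, which for gait velocity matches Aim 2's stated endpoint.

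With complete data, the week-4 estimate from this model equals that of the simple week-4 regression, whose type I error was about 5% in step 5. Error rates with missing visits were not simulated. All other modifiers can keep the five-measure model, and the SAP should state its Aim 2 covariance explicitly. If compound symmetry or a dichotomised baseline was intended, the SAP should say so instead.

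This should be specified before unblinded analysis. It needs no new data. The cost is SAP wording and a model form for these modifiers that differs from the rest of Aim 2. Under the linear-growth assumption in step 5, there is also some loss of power against a linear-time compound-symmetry model (43% against 52%).

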#### Background & Purpose of the Research

Describe the purpose, specific aims or objectives and specify the hypotheses or research questions to be studied:

Aim 1: Quantify the neurological and functional improvements due to BCI-FES dorsiflexion therapy compared to dose- and intensity-matched conventional therapy. Hypothesis: The neural repair mechanisms underlying BCI-FES dorsiflexion therapy will lead to improvements in neurological and functional outcomes that are greater and longer-lasting than those achieved by dose-matched conventional therapy. Aim 2: Identify stroke features that are linked to responsiveness to BCI-FES dorsiflexion therapy. Hypothesis: Based on preliminary studies, baseline gait velocity, dorsiflexion AROM/torque, TA muscle electromyogram (EMG) and motor evoked potentials, the magnitude of EEG alpha- and beta-band ERD/ERS during attempted dorsiflexion, and sensory function will influence the response to BCI-FES dorsiflexion therapy. Aim 3: Investigate the mechanism of action of BCI-FES dorsiflexion therapy. Hypothesis: BCI-FES therapy reinforces the connectivity between foot M1 and the  $\alpha$ -MN due to Hebbian plasticity. The study will have a significant impact in rehabilitative neuroscience, clinical neurorehabilitation,

Provide the scientific or scholarly rationale for the research and describe the relevant background information and the specific gaps in current knowledge that this study intends to address:

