
having TA EMG or no response (no detectable EMG activity after 4 attempts).

3. EEG features: Movement induced EEG ERD/ERS and its spatial distribution in  $\mu$  (8-12 Hz) and  $\beta$  (13-30 Hz) bands may change after stroke. Since BCI-FES therapy depends upon and possibly alters  $\mu$  and  $\beta$  modulation, it is important to understand how the baseline ERD/ERS magnitude affects response to the therapy. EEG prior to the first BCI-FES session will be taken from Aim 1.

4. Nottingham Sensory Score: Baseline sensory impairment, as assessed by the Nottingham sensory system, can help determine if BCI-FES therapy can circumvent this requirement or not. Note that subjects will be informed that they are to refrain from starting any additional new physical therapies or other studies in stroke recovery for the entire duration of the study (including post-therapy visits). Subjects will be informed that those who become involved in outside therapy will be removed from the study as this may confound the scientific results.

Aim 3 (Mechanism study, not a clinical trial): In order to elucidate the plasticity mechanism underlying BCI-FES therapy, it is necessary to compare BCI-FES therapy to a control. Hence, two new groups of chronic stroke subjects with foot-drop will be recruited (10 subjects each, same selection criteria as in Aim 1). The first group (Group 3), will undergo BCI-FES therapy as in Aim 1 (no concurrent physiotherapy). The second group (Group 4), will undergo BCI-robotic orthosis therapy. This comparison will allow us to determine if the mechanism of BCI-FES therapy is via enhanced sensory feedback, or via co-incident activation of upper and lower motor neurons. BCI-robotic orthosis therapy is similar to BCI-FES therapy, except that the FES system is replaced by a robotic orthosis that dorsiflexes the foot when attempted dorsiflexion is detected from EEG. The use of a BCI-robotic allows us to test if sensory feedback is the primary driver of the neurological improvements or if co-incident firing between the brain motor cortex and muscles is the primary driver. It should be noted that BCI-FES and BCI-robot therapies both provide sensory feedback, but only BCI-FES provides co-incident firing between the brain motor cortex and the muscles. The primary outcome examined here will also be gait velocity. Other secondary outcomes include gait endurance and TA volitional EMG, as described above.

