Assessments are done on the same schedule as in Aim 1. This device will be used because, unlike EMG, NIRS systems are optically based. This allows for continuous monitoring at the muscle while the FES system is in use. EMG systems do not allow for continuous measurements when using FES, given that EMG systems measure electrical activity at the muscle that cannot be separated from the electrical activity of the FES system. TR-NIRS data will

provide insight into the metabolic changes at the TA muscle that can be compared between patients in the BCI-FES and BCI-robotic orthosis groups. This data will not only aid the stroke research community but will also aid the rehabilitation field in understanding healing dynamics post injury. The coherence between the Cz EEG electrode and the TA EMG will be calculated, known as  $w$ . The correlation between gait velocity and  $w$  will be calculated across the entire duration of study for all subjects. This will be repeated for both BCI-FES groups and BCI-robotic orthosis groups. Comparing the correlation between these 2 groups can provide insight into which of the above mechanisms is primarily driving plasticity.

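### Aim 3 hypothesises that BCI-FES strengthens connectivity (w), but no between-arm comparison of w is planned; the w-by-group term tests a different question.

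*Combined protocol and SAP*

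**What the plan says.** Background & Purpose of the Research gives the Aim 3 hypothesis: "BCI-FES therapy reinforces the connectivity between foot M1 and the" alpha motor neuron, through Hebbian plasticity. Study Design explains why the arms should differ. Both therapies give sensory feedback, but "only BCI-FES provides co-incident firing between the brain motor cortex and the muscles". The measure is defined in the same section: "The coherence between the Cz EEG electrode and the TA EMG will be calculated, known as" w.

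The plan uses w in two ways.

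- **Regression** (Study Design, repeated under Statistical Considerations). For gait velocity, "the analysis will be based on a regression model with group", w and their interaction, adjusted for baseline gait velocity. The relationship is to be assessed "averaged over time after treatment, adjusted for baseline outcome measure". The secondary outcomes are related to w in the same way.
- **Correlation** (Study Design). Gait velocity is correlated with w over the whole study in each group, and "Comparing the correlation between these 2 groups can provide insight into which of the above mechanisms is primarily driving plasticity".

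There are two lists of Aim 3 secondary outcomes, and w is in neither. Statistical Considerations says "the secondary outcomes are ankle torque and active range of motion". Study Design says "Other secondary outcomes include gait endurance and TA volitional EMG, as described above". The power statement, 82% at n=20, is for an effect such as w by group.

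**The concern.** The hypothesis is about what treatment does to connectivity, so the direct randomised test has w as the outcome and arm as the factor. In the plan w appears only as a predictor or correlate of gait velocity, torque and range of motion. The w-by-group term is also an association with a variable measured after randomisation, so randomisation does not protect its interpretation.

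Two misreadings are at stake. A null interaction could be taken as evidence against reinforced connectivity when w did rise in the BCI-FES arm. A significant interaction could be taken as support when treatment did not change w.

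**Working it through.** **1. The plan's own figure.** Inputs from the power analysis: n = 20, R² of 0.16 for the effect of interest, R² of 0.5 for three other variables. Alpha is stated as 0.05 for Aims 1 and 2 only and is assumed here for Aim 3.

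- f² = 0.16 / (1 − 0.50 − 0.16) = 0.16 / 0.34 = 0.471
- λ = n × f² = 20 × 0.471 = 9.41
- F test on 1 and 15 df: power 81.8%, which reproduces the stated 82%.
- The progress report in the renewal form gives 10 subjects randomised in Aim 3. Then λ = 4.71, the test has 1 and 5 df, and power is 42%.

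Both figures belong to the interaction. Neither is power for an arm difference in w.

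**2. What the interaction tests.** The planned model is

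velocity = a + b₁·group + b₂·w + b₃·(group × w) + b₄·baseline velocity.

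The velocity–w slope is b₂ in the robotic orthosis arm and b₂ + b₃ in the BCI-FES arm. With equal slopes b₃ = 0, whatever the arm means of w.

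**3. Simulation with equal slopes.** The documents give no SD, arm difference or test–retest correlation for w, so all of these are assumed. Baseline w₀ has SD 1; w₁ = 0.6·w₀ + d·arm + noise of SD 0.8; v₁ = 0.9·v₀ + 0.5·(w₁ − w₀) + noise of SD 0.44. The table shows rejection at two-sided 5%, with arms of equal size. Ranges cover variation between simulation runs.

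| Arm difference d (SD of w) | w-by-group, n=20 | ANCOVA of w, n=20 | w-by-group, n=10 | ANCOVA of w, n=10 |
|---|---|---|---|---|
| 0.5 | 5% | 24–26% | 5% | 12–14% |
| 0.8 | 5% | 54% | 5% | 26% |
| 1.0 | 5% | 72% | 5% | 37% |
| 1.5 | 5% | 97% | 5% | 67% |

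Entering change in w instead of post-treatment w leaves the interaction at about 5% under the same model.

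**4. Simulation without equal slopes** (n = 20, other assumed models):

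- w differs by 1.3 SD, slopes 0.5 (robot) and 1 (FES): w-by-group rejects 26%.
- w differs by 1.3 SD, slopes 0 and 1: 71%.
- w differs by 1.3 SD, common slope, but little spread of w in the robot arm and measurement error in w: 14%.
- Velocity follows change in w and only FES subjects change (mean rise 0.25): about 5% if the rise is identical in all, 16–20% if its SD is 0.10, 37–48% if its SD is 0.20.
- **No** arm difference in w, slopes 0 and 1: w-by-group rejects 70%; a direct test of w rejects 5%.

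**The case against.** A reader might infer that Aim 3 as planned cannot detect its mechanism even when that mechanism is true. The documents do not support that, for three reasons.

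First, the 5% is a consequence of equal slopes, and the plan nowhere says that slopes are equal. Study Design sets up two rival drivers: feedback in both arms, and co-incident firing in BCI-FES only. If gains in the robotic orthosis arm come through feedback and bypass w, velocity should track w more closely under BCI-FES. A differing relation is then the intended contrast, and step 4 shows that the test has some power for it.

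Second, the whole-study correlation comparison is a separate analysis. A correlation, unlike a slope, rises with the spread of w, so it can differ between arms under one common slope. No test is named. Under one reading (7 visits, per-subject correlations, Fisher z, t-test between arms, common slope 0.5, a rise of 1.0–1.5 SD in BCI-FES only, assumed visit noise), it rejects 12–89% at n=20 and 9–56% at n=10 when velocity follows all variation in w.

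Third, Study Design labels Aim 3 a mechanism study and not a clinical trial, and a direct test of w with 10 subjects is weak unless the effect is large.

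These points stand. They limit the 5% claim and justify keeping both planned analyses. They do not fill the gap: neither analysis estimates the effect of treatment on w, and a difference in slope or correlation can arise with or without one.

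**Conclusion.** The concern holds in conditional form. No section plans a comparison of w between the randomised arms, although the hypothesis is an effect on connectivity and w is its measure. This rests on the text alone and needs no assumption.

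The w-by-group term tests a slope difference. It rejects at about 5% however far w rises **if** slopes are equal. When slopes differ it rejects more often, including when treatment does not move w. The correlation comparison may pick up part of the effect but does not estimate it. The 82% is arithmetically right for w-by-group at n=20 and does not carry over to the stated hypothesis or to 10 subjects. Every power figure for the direct test depends on the assumed effect size, the 0.6 correlation and equal arms.

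**What to change.** Add w as an Aim 3 outcome. Fit an ANCOVA of post-treatment w, averaged over the post-treatment visits, on randomised arm, adjusted for baseline w. Report the arm difference with its 95% CI as the direct test of the Aim 3 hypothesis, and state the alpha for Aim 3.

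Keep the w-by-group regression and the correlation comparison as the comparison of mechanisms, and name the test for the latter. Label the 82% as power for w-by-group at n=20, and give the figure of about 42% for the 10 subjects randomised.

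The cost is one extra model. Aim 3 assessments follow the Aim 1 schedule, which includes a baseline, and w is to be correlated with velocity over the whole study, so baseline w should be available; this needs confirming. The progress report lists data analysis as still to be completed. The result will be imprecise at n=10, so the estimate and its interval are the main product.
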